7.1.2 Schedule for Part 2: Child Pugh B Expansion Cohort

Study Event	Screening			Treat	ment Cycl	е		Safety F	ollow Up	Survival Follow Up
Time point (Cycle (C) & Day (D) or days after last dose)		C1D1	C1D15	C2D1	C2D15	C3+D1	C3+D15	30 days after last dose (SFUV1)	100 days after last dose (SFVU2)	Every 3 months after last dose
Window (days)	-28 to 1	-2 to +3	-2 to +3	-2 to +3	-2 to +3	-2 to +3	-2 to +3	±14	±28	±28
				Admin	istrative P	rocedures				
Informed consent & registration on OnCore®	x									
Eligibility determination	Х									
Prior and concomitant medication review	x	х	х	х	х	x	x	x	x	
Demographics & medical history	х									
HCC staging & liver disease history	х									
Confirmation of appropriate antiviral therapy if HBV+	х									
Enrollment	Х									
Subsequent Therapy								Х	X	
Survival status										Х
					Treatme	nt				
Sorafenib ¹		Х	Х	X	Х	X	Х			
Nivolumab ²		Х	Х	X	X	Х	X ²			
			Cli	nical pro	cedures a	nd assessme	nts			
AE monitoring	X	X	X	X	Х	X	X	X	X	
Compliance with oral study drug		X	х	Х	X	x		x		
ECG	Х									
Vital signs	Х	Х	Х	Х	Х	Х	Х	Х	X	
Complete physical examination	x	X	х	Х	X	x		x	x	
ECOG	Х	Х	Х	X	Х	Х		Х	X	
Liver function assessment (by Child Pugh Score)	x	x	x	x	x	x		x	x	

Study Event	Screening		Treatment Cycle					Safety F	Survival Follow Up	
Time point (Cycle (C) & Day (D) or days after last dose)		C1D1	C1D15	C2D1	C2D15	C3+D1	C3+D15	30 days after last dose (SFUV1)	100 days after last dose (SFVU2)	Every 3 months after last dose
Window (days)	-28 to 1	-2 to +3	-2 to +3	-2 to +3	-2 to +3	-2 to +3	-2 to +3	±14	±28	±28
Tumor imaging ³	X 3					X³ (every ±14 da		X³ (±28 days)		
			Laboratory	/ procedi	ires perfo	rmed at local	laboratory			
CBCD, CMP, PT/INR4	Х	X ⁵	X	Х	Х	Х	Х	X	X	
T3, fT4, TSH	Х	X ⁵		Х		Х		Х	Х	
Urinalysis	Х	X ⁵		Х		Х		Х	Х	
Pregnancy test in WOCBP only ⁶	х	х	Х	х	х	х	х	x	x	
Viral hepatitis viral load & serologic testing ⁷	X ⁷									
AFP ¹¹	Х	X ⁵		Х		Х		Х	Х	
Archival tumor sample8	Х							X8	X ₉	
PBMC sample ⁹	x	X ⁵	х	x	x	X (C3D1 and C7D1 only)		х		

Footnotes:

- 1. Sorafenib dose and schedule will be MTD from Part 1: Dose Escalation cohort and will be administered continuously. For patients enrolled to Part 2: Arm 1, sorafenib will start on C1D15. For patients enrolled to Part 2: Arm 2, sorafenib will start on C1D1.
- 2. Nivolumab will be administered at flat dose of 240 mg IV over 30 minutes every 14 days (-2 to +3 days) on D1 and D15 each cycle starting on C1D1. In Part 2 and with Study Chair approval, patients meeting criteria in Section 6.5 may switch to monthly dosing of nivolumab starting on or after C4D1 (-4 to +6 days) provided no uncontrolled or grade >2 immune related toxicity. A note to file must be included in study chart documenting Study Chair or designee approval. For patients who switch to monthly dosing on or after C4D1, the D15 visit and other assessments may be omitted if not clinically-indicated.
- 3. Cross-sectional imaging with CT or MRI abdomen plus pelvis (including triphasic/multiphase liver) and CT chest with or without contrast is required at screening and every 8 weeks ±14 days until end of treatment; ; at SFFUV1, imaging does not need to be repeated if performed within 28 days prior (±28 day window). Imaging may be performed more frequently if clinically indicated to evaluate for progression or toxicity. RECIST 1.1 measurements should be performed by a radiologist or qualified investigator at each time point.
- 4. Complete blood count and differential (CBCD), metabolic panel including liver and kidney function and electrolytes (see Section 7.3.6 for individual tests required), and PT/INR should be obtained as standard of care safety monitoring before every nivolumab infusion.
- 5. C1D1 blood tests and urinalysis do not need to be repeated if performed within 3 days before C1D1 during screening.
- 6. Perform on women of childbearing potential only at screening within 28 days, 24 hours prior to each nivolumab infusion (including C1D1), and at safety follow up visits. If urine pregnancy results cannot be confirmed as negative, a serum pregnancy test will be required.
- 7. Baseline hepatitis screening should be performed in all patients including HCV Ab, HBcAb total, HBsAg, and, in patients positive for HBcAb, HDV Ab. Prior serologic values collected within approximately 2 years may be used for screening if available. If HBcAb and/or HBsAg is positive, HBV DNA level by PCR should be monitored on treatment according to institutional standards (recommended is every 4 weeks according to treating investigator discretion) and patient should be treated with antiviral prophylaxis according to institutional practice. HCV RNA PCR should be monitored on treatment according to institutional practice. HBV DNA and HCV RNA should be checked and monitored in all cases of hepatotoxicity on treatment according to institutional standard practices.
- 8. Archival tumor samples (FFPE block when available and/or at least 10 unstained slides of approximately 10 µm thickness and at least 10 unstained slides of approximately 5 µm thickness plus a paired H&E slide) should be obtained from prior tumor sampling/diagnostic procedure(s) such as prior resection, core biopsy, or cytology/cell button when

UCSF Helen Diller Family Comprehensive Cancer Center

Version date: 03/09/2022 Protocol CC#: 174523

- available. FFPE block or slides should also be obtained from any subsequent tumor sampling which occurs during or after protocol therapy (such as repeat biopsy to confirm progression or palliative metastatectomy surgery). See Appendix 14.8.
- 9. Blood samples will be obtained in UCSF patients only for PBMC immune profiling at Screening, on Day 1 and 15 of Cycles 1 and 2, Day 1 of Cycles 3 and 7, then at SFUV1. See Appendix 14.8.
- 10. Removed.
- 11. AFP will be performed at screening, all cycles D1, at disease progression, SFVU1, and SFVU2.

7.2 Administrative procedures and data collection

7.2.1 Informed consent

The treating investigator must obtain documented consent from each potential subject prior to participating in a clinical trial.

7.2.1 Registration

All patients who consent will be registered in OnCore®, the UCSF Helen Diller Family Comprehensive Cancer Center Clinical Trial Management System (CTMS).

7.2.1.1 Sub-site registration

The sub-site must notify the UCSF Clinical Research Coordinator (CRC) and Study Chair of patient consent(s) at sub-site within 3 business days of consent. A study ID will be provided as confirmation of receipt which will enable registration on OnCore®.

7.2.2 Eligibility determination

All inclusion and exclusion criteria (see Section 5.1) will be reviewed and signed off on by the investigator or qualified designee at study site, and site study coordinator to ensure that the subject qualifies for the trial. For patients in screening at sub-site, the UCSF Study Chair or designee must review and confirm eligibility to prior to enrollment (see Section 7.2.6.1).

7.2.3 Prior and concomitant medications

The investigator or qualified designee will review prior medication use, including any protocol-specified washout requirement, and record prior medication taken by the subject within 28 days before starting the trial. Prior treatments for the disease for which the subject has enrolled in this study will be recorded separately and not listed as a prior medication.

The investigator or qualified designee will record medication, if any, taken by the subject during the trial treatment until approximately 100 days after last dose of study drug at the Safety Follow Up Visits (SFUV1 and SFUV2). All medications related to reportable SAEs should be recorded.

7.2.4 Demographics and medical history

Standard demographic information (e.g. age, gender, race/ethnicity) will be collected from medical records. Medical history findings (i.e. previous diagnoses, diseases or surgeries) meeting all criteria listed below will be collected:

Not pertaining to the study indication

- Start before signing of the informed consent
- Considered relevant to the study.

Detailed instructions on the differentiation between medical history and adverse events can be found in Section 7.4.1.

7.2.5 HCC staging and disease history

The investigator or qualified designee will obtain prior and current details regarding disease status, including HCC stage at enrollment, stage at diagnosis, diagnostic test(s), and site(s) of disease. Staging will be captured by both American Joint Committee on Cancer (AJCC) TNM staging (Appendix 14.4) and Barcelona Clinic Liver Cancer (BCLC) staging (Appendix 14.5).

7.2.5.1 Prior treatments for HCC

The investigator or qualified designee will review all prior cancer treatments including surgery, ablative treatments, arterial therapies (such as transarterial chemoembolization (TACE) or transarterial radioembolization (TARE)), or radiation. No prior systemic therapy for HCC is permitted by this protocol.

7.2.5.2 Liver disease history

The investigator or qualified designee will review liver disease history including risk factors for HCC (including viral hepatitis, alcohol use, non-alcoholic steatohepatitis or fatty liver disease diagnosis or risk factors, cirrhosis/fibrosis, autoimmune disease, any other prior liver injury). History of and any new episodes of esophageal varices, ascites, or encephalopathy will be documented at baseline, during treatment, and until the SFUV.

7.2.5.3 Subsequent therapy

The investigator or qualified designee will review all new anti-neoplastic therapy initiated after the last dose of trial treatment until approximately 100 days after last dose of protocol therapy at the SFUV1 and SFVU2. Once new anti-cancer therapy has been initiated or if transition to palliative/end of life care such as Hospice enrollment occurs, the subject will transition to the Survival Follow-Up Phase.

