4.3 Duration of Follow Up

Patients will be followed for survival every 3 months after completion of treatment or removal from study, or until death, whichever occurs first, for up to 2 years. Patients removed from study for unacceptable treatment related adverse event(s) will be followed until resolution or stabilization of all treatment related adverse events to Grade 2 or lower, or determination of chronic/irreversible by treating investigator and Study Chair.

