6.10 Discontinuation of therapy

Protocol treatment will be discontinued if criteria for withdrawal are met (Section 5.2) or for the following reasons:

- 1. Unacceptable toxicity attributed to either study drug (see Section 6.9)
- 2. Radiographic disease progression by RECIST 1.1
 - Subjects meeting criteria for treatment beyond progression may continue treatment until progression confirmed on one follow up imaging study, according to Section 6.11 below
- 3. Complete response after 24 months of protocol treatment

Follow up for protocol endpoints including safety and survival will continue per Section 7.1 after discontinuation.

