7.4 Assessing and reporting adverse events (AE)

All subjects who receive at least one dose of study treatment will be evaluable for safety from the time of informed consent until 100 days after last dose of protocol therapy or the start of a new anti-cancer therapy after study discontinuation, whichever is earlier. Any serious adverse events (SAE) occurring later than 100 days after the last dose of protocol therapy or after start of new anti-cancer therapy also should be recorded and reported if assessed as at least possibly related to study drug or a protocol-specified procedure. All observations pertinent to the safety of the study treatment will be recorded and included in the final report.

Safety variables include the following: AEs, laboratory changes (complete blood counts, electrolytes, chemistry, and coagulation) if determined clinically significant by treating investigator and/or Study Chair, changes in vital signs (blood pressure, heart rate, respiratory rate, and temperature), and in some instances, changes in imaging findings if indicative of a safety event.

All AEs whether considered drug-related or not, will be recorded in case report forms in the OnCore® CTMS including Grade, attribution to one or both study drugs, other attribution(s), start/stop dates, and whether serious and/or unexpected. For all events, the relationship to treatment and the intensity of the event will be determined by the investigator. This trial will use the NCI CTCAE v.4.03 (https://ctep.cancer.gov/) for assessment of toxicity and SAE reporting with regard to toxicity grade. Investigators should refer to the Safety Information section of the current IB for sorafenib and nivolumab, including the DCSI (development core safety information), for the expected side effects of the study drugs.

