7.4.2 Reporting of SAE to Bayer

All SAEs occurring from date of informed consent until 100 days after last dose of protocol therapy regardless of attribution should be reported to Bayer within 24 business hours/1 business day using a MedWatch Form 3500A (which can be accessed at http://www.accessdata.fda.gov/scripts/medwatch/ and in Appendix 14.9), using one of the mechanisms below. Any serious adverse events (SAE) occurring later than 100

days after the last dose of protocol therapy also should be recorded and reported if assessed as at least possibly related to study drug or a protocol-specified procedure.

Bayer SAE Electronic Mailbox:

Bayer SAE Facsimile:

Bayer USPS Address:

Global Pharmacovigilance - USA

Bayer Corporation

Reports for all Bayer products can also be phoned in via the Clinical Communications Dept.:

Bayer SAE Phone: (Medical Communications)

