8.2.1.2 Part 2: Child Pugh B Expansion Cohort primary endpoint

For Part 2: Child Pugh B Expansion Cohort, the primary endpoint is safety of the combination in patients with Child Pugh B liver function as measured by rate of grade ≥3 AE (CTCAE v. 4.03) assessed as at least possibly related to sorafenib, nivolumab, or the combination of therapies. Adverse events will be graded using NCI CTCAE v.4.03 (https://ctep.cancer.gov/). Relationship to sorafenib, nivolumab, or combination will be adjudicated by the treating investigator and/or Study Chair.

This is a pilot study. For Part 2, an acceptable rate of grade ≥3 treatment-related AE would be ≤ 50% based upon rate of treatment-related grade ≥3 AE of 24.5% of Child Pugh B7-8 HCC patients treated with nivolumab in the CheckMate 040 Child Pugh B cohort,³⁸ and 28% of Child Pugh B7-9 HCC patients treated with nivolumab in a retrospective institutional cohort,³⁹ along with rates of grade 3-4 treatment-related AE of 30-36% in Child Pugh B7-9 HCC in the GIDEON registry.⁴⁰

With an expected sample size of 12 patients with Child Pugh B7-9 HCC treated in Part 2, the 95% confidence interval (CI) for determining the rate of grade \geq 3 treatment-related AE if the actual rate is 50% will be (0.22, 0.78). If the actual rates are 30%, 40% or 60%, the 95% CI will be (0.07, 0.60), (0.14, 0.70) and (0.30, 0.86) respectively.

If the Child Pugh B Expansion Cohort end of enrollment date of 30 April 2022 is reached before completion of enrollment of n=12, rates of grade ≥3 treatment-related AE will be described along with 95% CI according to the sample size accrued at time of discontinuation (Table 8.2.1-1).

Table 8.2.1-1. Sample Size of Child Pugh B Expansion Cohort for Estimating Rate of Grade ≥3 TRAE.

Sample size in Child Pugh B Expansion Cohort	Actual rate of Grade ≥3 TRAE	95% CI
	30%	0.0, 0.71
6	40%	0.0, 0.71
O	50%	0.10, 0.90
	60%	0.30, 1.0
	30%	0.0, 0.55
0	40%	0.0, 0.71
8	50%	0.15, 0.85
	60%	0.29, 0.96
	30%	0.02, 0.58
10	40%	0.10, 0.71
10	50%	0.19, 0.81
	60%	0.30, 0.90
	30%	0.07, 0.60
12	40%	0.14, 0.70
12	50%	0.22, 0.78
	60%	0.30, 0.86

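### Hospice or palliative transition moves a patient to survival-only follow-up before day 100, in conflict with the safety window behind the Part 2 primary endpoint; the gap is narrow and cheap to close

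*Combined protocol and SAP*

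**What the plan says.** **The transition rule.** Section 7.2.5.3 (Subsequent therapy) names two triggers for leaving safety follow-up. One is the start of new anti-cancer therapy. The other is that "if transition to palliative/end of life care such as Hospice enrollment occurs, the subject will transition to the Survival Follow-Up Phase". No minimum safety period is given for either.

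**What the survival phase contains.** In the Part 1 and Part 2 schedules (Sections 7.1.1 and 7.1.2), the Survival Follow-Up column, every 3 months after last dose, is marked for "Survival status" and nothing else. AE monitoring, laboratory tests, physical examination and Child Pugh score are marked at the 30-day and 100-day safety visits and stop there.

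**The safety window.** Section 7.4 makes every dosed subject evaluable for safety from consent "until 100 days after last dose of protocol therapy or the start of a new anti-cancer therapy after study discontinuation, whichever is earlier". Hospice is not listed as an end. Section 6.10 adds: "Follow up for protocol endpoints including safety and survival will continue per Section 7.1 after discontinuation".

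**Serious events.** Section 7.4.2 covers "All SAEs occurring from date of informed consent until 100 days after last dose of protocol therapy regardless of attribution", with no hospice exception. Section 7.4.1.2 requires potential drug-induced liver injury to be handled as an SAE even when it is not serious by regulatory definition.

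**Unresolved related events.** Section 4.3: "Patients removed from study for unacceptable treatment related adverse event(s) will be followed until resolution or stabilization of all treatment related adverse events", or until judged chronic or irreversible.

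**The endpoint.** Section 8.2.1.2 defines the Part 2 primary endpoint as the "rate of grade ≥3 AE (CTCAE v. 4.03) assessed as at least possibly related to sorafenib, nivolumab, or the combination of therapies". It states that "an acceptable rate of grade ≥3 treatment-related AE would be ≤ 50" per cent. It gives no time window and no rule for patients whose safety follow-up is cut short.

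**The concern.** The two triggers in Section 7.2.5.3 share one sentence and one consequence. For new anti-cancer therapy, that consequence agrees with Section 7.4, where the window also ends. For hospice or palliative care it does not: Section 7.4 runs on to day 100, while the schedule the patient has been moved to contains no safety contact. A site can reasonably read the rule as ending the safety visits. With two sites in Part 2, each could defensibly follow a different section.

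The Part 2 primary endpoint is a safety rate, so incomplete ascertainment works in one direction only: an unseen event lowers the rate and moves it towards the acceptable side of the limit. Section 8.2.1.2 has nothing that would detect or adjust for this. Section 7.2.5.2 also documents new ascites, encephalopathy and varices only up to the safety follow-up visit, so that record can stop with the skipped visits.

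**Working it through.** **1. The sections side by side, for a patient who enters hospice on day d after last dose (d < 100, no new anti-cancer therapy)**

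| Source | What happens after day d |
|---|---|
| 7.2.5.3 | Moves to the Survival Follow-Up Phase |
| 7.1.1, 7.1.2 | That phase schedules survival status only |
| 7.4 | Still evaluable for safety to day 100 |
| 6.10 | Safety follow-up continues per Section 7.1 |
| 7.4.2 | All SAEs, any attribution, reportable to day 100 |
| 4.3 | If removed for unacceptable related AEs, followed to resolution, stabilization or a chronic/irreversible judgement |

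The period without a scheduled safety contact is 100 − d days. For d = 20, an illustrative value, it is 100 − 20 = 80 days.

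**2. Which events can be lost.** To change the primary rate, an event has to meet all of these conditions:
- it is grade ≥3 and at least possibly related (8.2.1.2);
- it is that patient's first such event, because a patient already counted cannot be counted again;
- it arises after the transition and by day 100;
- it is not an SAE, or it is an SAE that the site never hears of because the visits were skipped;
- it is not picked up by the follow-up in Section 4.3.

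A patient who leaves before completing one cycle because of unrelated liver-disease complications is outside the safety analyses (8.1.2) and is replaced (5.3.2), so does not enter this count.

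**3. The plan's own precision at n = 12.** Formula: p ± 1.96 × √(p(1 − p)/n), with p taken at the nearest whole number of patients.
- 50%: 6/12 gives (0.217, 0.783); the plan states (0.22, 0.78).
- 30%: 4/12 gives (0.067, 0.600); the plan states (0.07, 0.60).
- 40%: 5/12 gives (0.138, 0.696); the plan states (0.14, 0.70).
- 60%: 7/12 gives (0.304, 0.862); the plan states (0.30, 0.86).

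All four reproduce to two decimals.

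**4. Effect of a missed patient.** One patient is 1/12 = 8.3 points.
- True 7/12 (58.3%, above the limit) with one missed is observed as 6/12 (50.0%, at the limit).
- True 8/12 (66.7%) needs two missed to be observed as 6/12.

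**5. Sensitivity.** Let p be the true rate and q the share of event-patients missed. The observed count is then Binomial(12, p(1 − q)). The documents give no value for q, so those below are assumptions.

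| True rate | q = 0 | q = 5% | q = 10% | q = 20% |
|---|---|---|---|---|
| 60%: P(observed ≤ 6/12) | 0.335 | 0.417 | 0.501 | 0.666 |
| 70%: P(observed ≤ 6/12) | 0.118 | 0.181 | 0.259 | 0.445 |

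Given the conditions in step 2, the low end of the range for q is the more plausible. Even with nothing missed, a true rate of 60% gives an observed rate within the limit one time in three.

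**The case against.** The strongest reply is that Section 7.2.5.3 concerns the recording of later treatment and says nothing about AE collection. Section 7.4 governs safety recording, its duty to record all AEs is unaffected, and only scheduled visits are dropped. Sparing hospice patients clinic visits is a reasonable choice about burden. Most events of real concern are serious, and these remain reportable. Weekly review of AEs from both sites at the coordinating centre (Appendix 11, 3.1) gives further consistency. The 50% figure carries no test or stopping rule, and an 8.3-point shift is small beside an interval of 0.22 to 0.78.

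Much of this stands. A reader might infer that the AE record closes at hospice entry; no section says so. A reader might infer that related hepatic events in the sickest patients vanish. But potential drug-induced liver injury is handled as an SAE. A patient who stops treatment with related grade ≥3 decompensation has already been counted, and later worsening cannot change a per-patient rate. It is also tempting to state what fraction of the 12 patients is exposed, but the documents give no hospice rate, and a hospice entry is not a missed event.

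Three parts do not stand. A duty to record does not replace the contact at which the site learns of the event. Weekly review covers only events already entered. And a wide interval describes sampling error; it does not allow for an under-count that always runs the same way.

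**Conclusion.** The conflict is real and confined to patients who enter hospice or palliative care within 100 days of last dose without starting new anti-cancer therapy. What it exposes is mainly a first, non-serious, related grade ≥3 event after the transition, plus the loss of the scheduled contacts through which any event would come to light. The direction is certain: a loss can only lower the Part 2 primary rate. The size per missed patient is 8.3 points at n = 12. How often it would happen cannot be computed from the documents and is probably low. That hospice patients are especially prone to late related events is a plausible inference, not something the plan states. The documents do not support a claim that the primary result is materially biased or that the 50% limit would be wrongly met. Severity is minor to moderate: worth correcting because the correction is cheap and the denominator is 12.

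**What to change.** 1. Reconcile Sections 7.2.5.3, 7.4, 7.4.2, 6.10 and both schedules so that hospice or palliative transition ends clinic visits but not AE and SAE collection, which continues to day 100 by telephone or record review. Add a matching AE entry to the schedules for these patients.
2. State the time window of the primary endpoint in Section 8.2.1.2, in line with Section 7.4.
3. Report the number of patients with safety follow-up shorter than 100 days and the reason, with a sensitivity analysis of the primary rate. A simple version counts each such patient without a recorded qualifying event as having had one, which gives an upper bound beside the observed rate.

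**Cost.** An amendment sentence and one or two remote contacts per affected patient, with no new visits or procedures. The observed rate may come out slightly less favourable. Events visible only in laboratory results may still be missed, because no blood would be drawn; the sensitivity analysis in item 3 is what covers that remainder.
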